11.3 Evaluation of symptom data (MDASI-BT)

The sample size for this trial was based on the primary end point of the study.

Received MDASI-BT forms will be checked versus the timing schedule and considered as valid if they fall within one week of the scheduled assessment. Compliance rates will be calculated as the number of received valid forms over the number of expected forms. Differences between groups in compliance will be tested by use of Fisher's exact test at every time point.

Estimates of differences in the mean symptom severity and mean symptom interference between groups will be estimated in the intent to treat population. All patients with at least one valid MDASI-BT will be included in the analyses. MDASI-BT completed at study registration will be considered baseline. All MDASI-BT data received after randomization will be used in the primary analyses.

For the MDASI-BT, differences of at least 2 points will be classified as the minimum clinically meaningful change in the symptom severity and symptom interference measures. For example, an increase of 2 points or more would mean a moderate improvement, whereas a decrease of 2 points or more would be interpreted as moderate worsening. For individual symptoms, a rise in a symptom score means deterioration, whereas a reduced score means improvement of the specific symptom.

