1.2 Phase II

Primary endpoint:

1. To determine the efficacy of vorinostat + cRA, versus TMZ + cRA, versus vorinostat + cRA + TMZ in patients with recurrent glioblastoma multiforme as determined by Progression Free Survival (PFS) using an adaptive randomization phase II trial design.

Secondary endpoints:

- 2. To determine the radiological response, progression free survival at 6 months, overall survival and unexpected toxicity in the three treatment arms.
- 3. To obtain exploratory data regarding histone 3 and 4 acetylation and p21 levels in tumor tissue and peripheral monocytes in a subset of surgical patients and in non-surgical patients with available tissue from prior surgical interventions.
- 4. To evaluate the occurrence of symptoms and correlate to disease progression and tolerance to treatment using the MD Anderson Symptom Inventory-Brain Tumor Module (MDASI-BT) self-reporting tool.

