
2.10 Rationale for Symptom Assessment Evaluation

Glioblastoma multiforme is a highly malignant type of tumor with recognized impact on the patients' physical, and neurologic function [29]. Most patients do succumb to their illness within two years. This study seeks to improve on these clinical results, hypothesizing that using a combination of cytotoxic and cytostatic agents will result in improved survival. However, given the intensive nature of this regimen, it will be important to determine whether any survival benefit is associated with an improvement in symptoms or is the increase in survival offset by a worsening of these parameters. Precedence for measuring "non-therapeutic" endpoints exists in oncology research. For example, Gemcitabine was approved by the FDA partially as a consequence of the decrease in pain reported in pancreatic patients who were treated, not on the basis of survival improvement which was modest, at best [30]. There have been efforts in neuro-oncology to evaluate secondary endpoints using validated instruments as an additional indicator of benefit.

The M.D. Anderson Symptom Inventory-Brain Tumor Module (MDASI-BT) allows the self reporting of symptom severity and interference with daily activities. It has demonstrated reliability and validity in the primary brain tumor patient population [31]. This tool represents a modification of the widely used and validated MDASI, with particular attention to symptoms common in patients with brain tumors. The availability of validated instruments provides an opportunity to prospectively assess the impact of treatment, both positive and negative, on patients. This evaluation of symptom burden in this study will assist in finding the best possible treatment with the least toxicity.

2.11 Preliminary Data from recently completed Phase I trial of vorinostat, isotretinoin and Carboplatin

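### Section 11.3 reverses the direction of the MDASI-BT summary scores: a rise of 2 points in symptom severity or interference is called improvement, against the next sentence of the same paragraph

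*Combined protocol and SAP*

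**What the plan says.** Objective 4 of Section 1.2 makes symptoms a secondary endpoint of the phase II component: "To evaluate the occurrence of symptoms and correlate to disease progression and tolerance to treatment", using the MDASI-BT. Section 2.10 describes the tool as one that "allows the self reporting of symptom severity and interference with daily activities". It explains that the assessment should show whether a survival gain comes with better symptoms or is offset by worse ones.

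Section 11.3 sets out the analysis in three steps:

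- The quantities compared: "Estimates of differences in the mean symptom severity and mean symptom interference between groups will be estimated in the intent to treat population".
- The threshold: "differences of at least 2 points will be classified as the minimum clinically meaningful change in the symptom severity and symptom interference measures".
- The direction, given as an example for those measures: "an increase of 2 points or more would mean a moderate improvement, whereas a decrease of 2 points or more would be interpreted" to mean a moderate worsening.

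The paragraph then closes with a second direction rule, limited to single symptoms: "For individual symptoms, a rise in a symptom score means deterioration, whereas a reduced score means improvement of the specific symptom".

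**The concern.** The two direction rules stand next to each other and point opposite ways. Severity and interference are burdens, so a higher score should mean a worse state, as the rule for single symptoms says. The rule for the summary measures says the reverse.

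This matters because the example is the only place where the plan says which direction of the summary scores counts as benefit. An analyst who programs or writes up the 2-point classification from Section 11.3 has no other rule to follow. An arm whose patients report a growing symptom burden would then be described as improving, and an arm that relieves symptoms as worsening. That would give the wrong answer to the question in Section 2.10, whether longer survival is bought with worse symptoms.

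**Working it through.** The plan gives no figure to reproduce, and no sample size, power or event count is involved. The check compares the two rules and uses one identity about means.

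**Inputs, all from Section 11.3 except the last**

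| Item | What the plan gives |
|---|---|
| Meaningful change | 2 points, for the severity and interference measures |
| Rule A (severity and interference measures) | up by 2 or more = moderate improvement; down by 2 or more = moderate worsening |
| Rule B (individual symptoms) | up = deterioration; down = improvement |
| Summary measures | mean symptom severity, mean symptom interference |
| What is reported (Section 2.10) | severity of symptoms and interference with daily activities |

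**Step 1. How a mean moves.** Take mean severity as the unreversed mean of k symptom scores and let d1, ..., dk be a patient's changes from baseline. The change in the mean is (d1 + ... + dk)/k.

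**Step 2. All symptoms rise by 2.** The change in the mean is (2 × k)/k = 2, whatever k is. Under Rule B all k symptoms have deteriorated. Under Rule A mean severity shows a moderate improvement.

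**Step 3. All symptoms fall by 2.** The change in the mean is (−2 × k)/k = −2. Under Rule B all k symptoms have improved. Under Rule A mean severity shows moderate worsening.

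**Step 4. Not only a matter of extreme cases.** If the mean rises by 2 or more, at least one symptom must itself have risen by 2 or more; if every change were below 2, their mean would be too. So Rule A can never call mean severity improved unless at least one symptom has deteriorated under Rule B by the full threshold.

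**Step 5. Could both rules hold?** Only if the summary were reverse-scored, for instance as a constant minus the mean, so that higher meant better. Neither Section 11.3 nor Section 2.10 describes such scoring. The names used, severity and interference, describe scores that rise as the patient gets worse.

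**Step 6. Interference.** Rule B speaks of symptoms, and interference with daily activities is not a symptom item, so Steps 2 to 4 apply strictly to severity. For interference, higher being worse follows from the name of the measure and its description in Section 2.10. Rule A treats both measures alike, so it has the same sign problem for both.

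**The case against.** The wording error itself is hard to contest. The strongest case on the other side is that its consequences are small.

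- **No responder analysis is planned.** Section 11.3 defines no proportion improved or worsened and no test of one. The planned estimates are differences in means, and they keep their value and sign whatever label is attached. This stands: the reversal affects labelling and interpretation, not the estimates.
- **It is only an example, and the contradiction would be noticed.** It may well be noticed, but no other text gives a direction for the summary measures. Leaving the choice to the analyst after the data are in is what a plan is meant to avoid.
- **The two rules have different scopes.** This is formally true. It does not help for severity, which is made of the symptom scores. For interference the proof is weaker, but no ordinary reading makes more interference with daily life an improvement. If a transformation is intended, the plan must state it, so the text has to change either way.
- **The measure drives no decision.** The MDASI-BT is optional and needs consent (notes to Sections 6 and 7). Section 8.0 does not list it among the secondary endpoints, although Section 1.2 does. Randomization, arm dropping and selection rest on PFS; toxicity stopping rests on DLTs. This stands and limits the reach of the error.
- **The objective concerns occurrence and correlation.** A correlation with the raw score does not depend on the label. This is right for Section 1.2, but Section 2.10 does ask about improvement against worsening.
- **It is unclear whether the 2 points are a change within a patient or a difference between groups.** This is a fair observation, but the direction is reversed on either reading.

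**Conclusion.** The concern holds. In the current text of Section 11.3 the direction rule for the MDASI-BT severity and interference measures has the wrong sign and contradicts the sentence that follows it.

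The size is a complete reversal of labels: followed literally, each change of 2 points or more in either summary is classed opposite to its meaning. Changes below 2 points, raw mean differences and everything based on PFS are untouched. The 2-point threshold is not in question.

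The conclusion assumes that the summaries are unreversed means of the item scores; the documents describe no other scoring. For severity the contradiction then follows from the plan's own text. For interference it rests on the meaning of the measure. Because the rule is the only one given and would misstate benefit and harm on a secondary endpoint, it should be corrected and not left to the analyst's judgement.

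**What to change.** In Section 11.3, replace the example with a rule such as: a rise of 2 points or more in mean symptom severity or mean symptom interference is moderate worsening, and a fall of 2 points or more is moderate improvement. Extend the closing sentence to the interference items, so that all scores share one stated direction.

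If the summaries are meant to be transformed so that higher is better, give the formula and say that the direction differs from that of the single items.

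The change is one or two sentences. It alters no sample size, visit, form or data collection. Make it before symptom data are examined by arm, so that nobody can suggest the direction was chosen afterwards.

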12.0 COMPLIANCE AND DATA MANAGEMENT

12.1 Protocol Compliance:

The attending physician and oncology research nurse must see each patient after the first cycle, and subsequently after each 2 cycles of treatment prior to initiating the next cycle. All required interim and pretreatment data should be available and the physician must have made a designation as to tumor response and toxicity grade.

12.2 Data Entry:

All data will be entered on the computerized Protocol Data Management System (PDMS) of the Division of Medicine at MDACC. Patients must be registered in PDMS before a course of therapy can be given. A brief explanation for required but missing data should be recorded as a comment.

12.3 Accuracy of Data Collection:

A group consisting of the study chairman, the department chairman, the deputy chairman and an faculty member from the neuroradiology department will be the final arbiter of response or toxicity should a difference of opinion exist. The study chair will have the deciding vote in case of a tie.

Any life-threatening and/or unexpected and serious (grade 3 or 4) toxicity will be reported within 5 working days to the Study Chairman who, in turn, must notify the Surveillance Committee and the sponsoring agencies (See Appendix A).

